#### 8.1.3 Visit 2: Surgery

*[Purpose: To collect data on the performance of intra-operative molecular imaging]*

1. AEs and ADEs will be recorded during and following surgery.

03 Sep 2025

2. After the surgical site is visualized under normal light and/or palpation, the number and location of suspect lesions detected under normal light will be recorded on the schematic using an “O”.
3. Following the assessment by normal light, subjects will undergo fluorescence imaging of the surgical field. Suspect lesions detected under fluorescence imaging will be marked on the schematic using an “X”.
4. All identified suspect lesions will be marked on the schematic (“O”, “X”, or “⊗” as described in [Section 4.1.3](#)) and excised, at the discretion of the Investigator.
5. Sentinel lymph node biopsy will be performed at the Investigator’s discretion per the standard of care.
6. All excised lesions will be sent to the local laboratory for histopathology and immunohistochemistry staining. A unique identifier will be assigned to each excised lesion and the location of each will be recorded along with the unique identifier. If an organ/large section of tissue (e.g. uterus, omentum) with multiple lesions is excised *in toto*, one grossly positive lesion will be utilized for the purposes of calculating sensitivity and FR expression.
7. Histopathology, folate receptor expression, and genomic testing results will be recorded once data is received per institutional practices and timeline.

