#### 4.1.3 Surgical Procedure

All subjects participating in the study are expected to receive CYTALUX™ (pafolacianine) injection and standard care surgical evaluation of disease. Intraoperative imaging will be completed between one and one hundred sixty-eight hours after CYTALUX™ (pafolacianine) infusion is completed. Any tissues removed as part of standard of care will undergo assessment with NIR light imaging prior to and after resection. This will be then compared to gold standard histologic confirmation by pathology.

After the surgical site is visualized, location of the primary tumor and any clinically suspected additional tumors detected under normal light and/or palpation/endoscopic visualization will be recorded photographically or by video as per surgeon's standard clinical practice. Tumors detected under normal light will be indicated by an "o" on the image as well as on the schematic.

Once normal light assessment is completed, the surgical field will be visualized using an NIR imaging system under fluorescence. Any tumor and/or nodules detected using the NIR imaging system will be recorded on the intraoperative schematic using an "X". Those areas that were also identified under normal light, the "X" will be superimposed on the "O" as "⊗". For nodules identified only under fluorescence, they will be recorded only by an "X".

Light source	Notation
Visible light	O
Fluorescent	X
Both	⊗

03 Sep 2025

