#### **4.1.4     *Surgical Tissue Processing – Resected Lesions and Lymph Nodes***

Each lesion obtained for evaluation will be sent to local pathology for processing according to their standard practice. An inventory of specimens sent to local pathology labeled as above will be maintained.

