### **6.3 Measures to Minimize Bias – Randomization and Blinding**

This trial will be an open-label study with no randomization or blinding. All subjects will receive the study drug.

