## 9 STATISTICAL CONSIDERATIONS

### 9.1 Statistical Hypotheses

- Primary Efficacy Endpoint:
  - The primary efficacy endpoint is the sensitivity of CYTALUX with NIR imaging for detection of malignant lesions. Sensitivity is defined as the proportion of fluorescent light positive lesions that are histologically confirmed to be cancer relative to the total number of lesions confirmed to be cancer.  
Sensitivity = (True Positive)/(True Positive + False Negative)
- Secondary Efficacy Endpoints:
  1. Incidence rates of all adverse events (AEs), adverse device effects(ADEs), and SAEs, from the time of CYTALUX administration through Visit 3
  2. Sensitivity for cancerous lesions for:
    - a. FR $\alpha$  positive lesions
    - b. FR $\beta$  positive lesions
- Exploratory Endpoints:
  1. Genomic evaluation of tumor inclusive of, but not limited to:
    - a. Estrogen receptor/progesterone receptor (ER/PR) status
    - b. HER2 status
    - c. Mismatch repair (MMR) status
    - d. POLE status
    - e. p53 status
    - f. CARIS whole genome sequencing
  2. The exploratory endpoint is the detection rate of CYTALUX with NIR imaging for identification of SLNs. The detection rate is the proportion of the patients with SLNs detected by CYTALUX and NIR imaging in all enrolled patients.

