### **9.2.2 Analysis of the Primary Efficacy Endpoint**

The primary analysis of the primary endpoint will include subjects exposed to CYTALUX™ (pafolacianine) injection and undergo fluorescent imaging (CYTALUX™ (pafolacianine) injection+Imaging) who:

- Received study drug and were evaluated under NIR fluorescent light imaging during surgery

The primary analysis of the efficacy endpoint will be a one-sample test for a proportion via an exact binomial test conducted at the two-tailed alpha level of 0.05. The test will compare the observed proportion against a threshold of 0.10. The efficacy of CYTALUX™ (pafolacianine) injection in combination with fluorescent imaging will be confirmed if the null hypothesis is rejected and the observed proportion is greater than 0.10. The two-sided 95% confidence interval (CI) will also be calculated.

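### The en-bloc rule in section 8.1.3 lets the one counted lesion be chosen with its fluorescence already known, and the sensitivity definition does not carry the rule

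*Protocol*

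**What the plan says.** Protocol section 8.1.3, step 6, sets a counting rule for specimens removed whole that contain multiple lesions, naming uterus and omentum as examples: "one grossly positive lesion will be utilized for the purposes of calculating sensitivity and FR expression". The rule names no selector and no time of selection, and gives no way to choose among several qualifying lesions.

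Four other places bear on what is known by then:

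- Section 8.1.3, step 3: "Following the assessment by normal light, subjects will undergo fluorescence imaging of the surgical field". Lesions seen this way are marked on the schematic, and excision follows in step 4.
- Section 4.1.3: "Any tissues removed as part of standard of care will undergo assessment with NIR light imaging prior to and after resection".
- Section 4.1.4: "An inventory of specimens sent to local pathology labeled as above will be maintained". The notation set out just before this, in section 4.1.3, is the O/X scheme for visible light and fluorescence.
- Section 6.3: "This trial will be an open-label study with no randomization or blinding".

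Sections 1.1, 3 and 9.1 define sensitivity as fluorescent confirmed cancers "relative to the total number of lesions confirmed to be cancer", with no exception for en-bloc specimens and no reference to section 8.1.3. The secondary endpoint ("Sensitivity for cancerous lesions for" FRα-positive and FRβ-positive lesions) does not mention the rule either. Section 9.2.2 takes the proportion into an exact binomial test: "The test will compare the observed proportion against a threshold of 0.10".

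**The concern.** Sensitivity is the share of counted cancers that fluoresced. If the lesion to be counted is picked by someone who already knows which lesions fluoresced, the choice can depend on the outcome being measured. Preferring a fluorescent lesion raises the estimate, and preferring a non-fluorescent one lowers it. In an unblinded study of an imaging agent, the upward direction is the more plausible.

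The primary estimate, its test against 0.10 and the two FR-subgroup sensitivities all depend on this choice. Section 9.2.2 treats rejection of the null, with an observed proportion above 0.10, as confirmation of efficacy. With 10 patients planned, a few selections can decide that result.

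There is a second, smaller problem. A reader of sections 1.1, 3 or 9.1 would count all confirmed cancers, while a reader of section 8.1.3 would count one per en-bloc specimen. The specific rule most plausibly governs, but the endpoint definition does not say so.

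**Working it through.** **Order of events.** Visible-light marks come first, then NIR marks, then excision, then NIR imaging of the resected tissue, then pathology. No step hides the NIR result from whoever selects the lesion. The visible-light marks are made before NIR imaging and could have anchored the choice, but step 6 does not use them.

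**Nothing to reproduce.** The protocol gives no lesion count, no expected sensitivity and no power, so the figures below are illustrations.

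**Inputs from the protocol.** 10 patients (section 1.1); null value 0.10 and an exact binomial test at two-sided 0.05 (section 9.2.2).

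**Assumptions.** One counted lesion per patient, so n = 10. Each counted lesion comes from an en-bloc specimen holding m = 3 cancers, unless stated otherwise. True per-lesion sensitivity is p.

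**Rejection rule.** Exact two-sided p-values against 0.10 with n = 10 are 0.0702 at 3/10, 0.0128 at 4/10 and 0.61 at 0/10. The test therefore rejects upward at X ≥ 4 and cannot reject downward.

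**Probability q that the counted lesion is fluorescent**

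- Choice unrelated to fluorescence: q = p.
- Fluorescent lesion always chosen when present, independent lesions: q = 1 − (1 − p)³. At p = 0.10, 1 − 0.9³ = 0.271. At p = 0.50, 1 − 0.5³ = 0.875.
- The same choice with within-specimen correlation ρ (beta-binomial, a = p(1−ρ)/ρ, b = (1−p)(1−ρ)/ρ): q = 1 − b(b+1)(b+2)/[(a+b)(a+b+1)(a+b+2)]. At p = 0.10 this gives 0.208 (ρ = 0.3) and 0.1735 (ρ = 0.5). At p = 0.50 it gives 0.7625 and 0.6875.
- Weak preference (a fluorescent lesion sought in 25% of selections, independent lesions): 0.75 × 0.10 + 0.25 × 0.271 = 0.143; 0.75 × 0.50 + 0.25 × 0.875 = 0.594.
- Only n₁ of the 10 patients have such a specimen (always chosen, independent): X is Binomial(n₁, 1 − (1 − p)³) plus Binomial(10 − n₁, p). At p = 0.50 the mean proportion is (5 × 0.875 + 5 × 0.50)/10 = 0.6875 for n₁ = 5, and (3 × 0.875 + 7 × 0.50)/10 = 0.6125 for n₁ = 3.

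**Results**

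| How the lesion is chosen | P(X ≥ 4) when true sensitivity is 0.10 | Expected reported sensitivity when truth is 0.50 |
|---|---|---|
| Unrelated to fluorescence | 0.013 | 50% |
| Fluorescent always, independent (worst case) | 0.275 | 87.5% |
| Fluorescent always, ρ = 0.3 | 0.136 | 76% |
| Fluorescent always, ρ = 0.5 | 0.079 | 69% |
| Weak preference (25%) | 0.043 | 59% |
| Fluorescent always, 5 of 10 patients affected | 0.091 | 69% |
| Fluorescent always, 3 of 10 patients affected | 0.047 | 61% |

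The bias can also run the other way. If a non-fluorescent lesion were always chosen when present (independent, m = 3), a true 50% would be reported as 0.5³ = 12.5%.

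**The case against.** The strongest reply is that *grossly positive* most naturally means macroscopically evident. That is a criterion in itself and does not depend on the NIR signal, so a lesion seen only under fluorescence would not qualify. This stands, and it narrows the problem to the choice among several macroscopically evident lesions in one specimen. It does not remove the problem, because that choice is exactly what step 6 leaves open.

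It can also be said that the text does not show that fluorescence is known for every lesion inside a uterus or omentum removed whole, that the labelling phrase in section 4.1.4 is ambiguous, and that pathology might choose without seeing the NIR marks. All of that is possible. The point is only that the rule permits a choice made with the result known, and no other section prevents it.

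The SAP, which is not shown, could add a tie-break. However, the lesion is chosen at surgery or in pathology, and an analysis plan cannot restore neutrality once a choice has been made with fluorescence known.

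The illustration rests on assumptions, and the analysis may contain more than 10 lesions. The error probabilities apply only if true sensitivity is 0.10. At a true 0.50, the 10-lesion test already rejects with probability 848/1024 = 0.83 without any selection, so there the main harm is to the estimate. Both remarks are fair.

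Finally, the mismatch with the definitions is largely a missing cross-reference, since step 6 states that it applies to the sensitivity calculation. That is accepted, and it is why the choice of lesion is the main defect.

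**Conclusion.** The concern holds. Section 8.1.3 fixes a counting rule for the primary endpoint that can be followed to the letter while the index lesion is picked on its fluorescence. The endpoint definition in sections 1.1, 3 and 9.1, and the test in section 9.2.2, do not carry that rule.

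Under the stated assumptions, selection towards fluorescence raises the chance of a false confirmation from 0.013 to between 0.043 and 0.275, and shifts a true 50% to between 59% and 87.5%. The upper ends are worst cases. Several of the milder scenarios stay near or below 0.05 on the test but still overstate sensitivity by 9 to 19 percentage points. The number of lesions per specimen, their correlation, how often the rule will apply and the way lesions will be chosen are all unknown, so the documents support neither a direction nor a size for any actual bias. The change should be made, but the point does not invalidate the study.

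**What to change.** - Write the en-bloc rule into the sensitivity definition in sections 1.1, 3 and 9.1, and refer to it in section 9.2.2, so that one denominator applies throughout, including for the FR subgroups.
- Define *grossly positive* as macroscopically evident tumour.
- Fix the index lesion by a rule independent of fluorescence, for example the largest malignant lesion at routine gross pathology, chosen without reference to the NIR marks and before the specimen is matched to the schematic. Record which lesion was chosen.
- Optionally, report sensitivity over all separately identified malignant lesions, with patient-clustered intervals, as a supporting analysis.

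The cost is protocol wording and one recorded field, with no extra staff or procedure, although pathology must make the choice before matching to the schematic. The estimate may be lower than under a free choice. A largest-lesion rule removes selection on fluorescence but still leaves smaller lesions out, so the result should be described as sensitivity for the index lesion in such specimens. The optional all-lesion analysis would address that, at the price of some further recording and matching.

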#### **8.1.4 Follow-Up Visit (4 weeks, +/- 1 week)**

*[Purpose: To evaluate subjects for any new adverse experiences, and to ascertain the status of previously unresolved AEs]*

This visit may take place in person or over the phone.

1. Inquire about new and unresolved AEs and ADEs

## **8.2 Efficacy Assessments**

### **8.2.1 Surgical Reporting Schematics**

Surgical Schematics will be used to record the lesions for each patient (see [APPENDIX 1](#)).

### **8.2.2 Pathology Samples**

All excised lesions will be processed according to local pathology practices. The final pathology results will be recorded in the CRF.

## **8.3 Adverse Events and Serious Adverse Events**

### **8.3.1 Definition of Adverse Events (AE) and Adverse Device Events (ADE)**

An AE is any untoward medical occurrence temporally associated with the use of an investigational medicinal product, whether or not considered causally related to that product. An AE can be any unfavorable and unintended sign (for example, an abnormal laboratory finding), symptom, or disease. The Investigator, or his/her designee, will document AEs. Only AEs and ADEs considered causally related to the investigational product will be documented during the trial period.

03 Sep 2025

An ADE is an AE associated with exposure to a medical device, such as the camera system and NIR illumination in this study. Where the abbreviation AE is used in this protocol, it can be understood to incorporate ADEs where appropriate.

The Investigator should use his/her discretion in ordering additional tests as necessary to monitor the resolution of such events. Event outcome at resolution or at time of last follow up will be recorded as event resolved, resolved with sequelae, ongoing at discontinuation, or death. Events ongoing after the subject's last visit will be followed per the investigator's standard of care.

The Investigator should consider AEs both as they relate to the investigational product and as they relate to the procedures involved in the trial. The Investigator is responsible for determining the initial relationship and severity of adverse events.

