## 2.4 Risk/Benefit Assessment

### 2.4.1 Known Potential Risks

The safety of CYTALUX was evaluated in four open label clinical studies, two studies (N = 44 and N = 150) in patients with ovarian cancer and two studies (N = 100 and N = 112) in patients with known or suspected cancer in the lung. A total of 406 patients received 0.025 mg/kg of CYTALUX via intravenous administration. Adverse reactions that occurred in  $\geq 1\%$  of patients were: nausea (13%), vomiting (5%), abdominal pain (2%), flushing (2%), other infusion-related reactions (2%), hypersensitivity (2%), elevation in blood pressure (1%), dyspepsia (1%), and chest discomfort (1%). Adverse reactions occurred during the administration of CYTALUX in 17% of patients. During the administration of PAFOLACIANINE, interruption of the infusion and/or treatment with an anti-histamine may be required in subjects who experience symptoms suggestive of hypersensitivity, followed by an observational period until the symptoms resolve. Anti-nausea (e.g. Zofran) and anti-histamine (e.g. benadryl) are frequently dosed prior to infusion of Pafolacianine in clinical practice to limit side effects. Symptoms to be aware of may include but are not limited to flushing, nausea, vomiting, abdominal pain and pruritis/urticaria. Other risks to subjects may include injection site adverse reactions (infusion and venous blood sampling), such as infection and hematoma. The use of a near-infrared fluorescence camera system during surgery may result in contamination of the sterile field or injury due to disengagement of the imaging device component coming in contact with the patient and/or surgical team. No clinically meaningful changes in vital signs, laboratory parameters, or electrocardiograms have been observed. Adverse events in the prior studies have been attributable to the underlying disease or to surgery (most commonly lymphedema, post-procedural hematoma, or urinary incontinence). Overall, the administered doses of PAFOLACIANINE have been well tolerated. The time spent visualizing the surgical field under NIR is quite short, with no meaningful prolongation of anesthesia. There are no known hazards associated with exposure of tissue to near-infrared light for short periods of time.

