### 3 OBJECTIVES AND ENDPOINTS

OBJECTIVES	ENDPOINTS
Primary	
To assess the ability of CYTALUX™ (pafolacianine) injection used with near-infrared (NIR) fluorescent imaging for the detection of malignant tissue in subjects undergoing surgical resection for endometrial cancer	
Sensitivity is defined as the proportion of fluorescent light positive lesions that are histologically confirmed to be cancer relative to the total number of lesions confirmed to be cancer.
 
Sensitivity = (True Positive)/(True Positive + False Negative)

Secondary	

 
1. To assess the safety of CYTALUX in subjects undergoing surgery for endometrial cancer
 
2. To assess folate receptor (alpha and beta expression) in resected specimens
 
	
 
1. Incidence rates of all adverse events (AEs), adverse device effects (ADEs), and SAEs, from the time of CYTALUX administration through Visit 3
 
2. Sensitivity for cancerous lesions for: 
 
a. FR<math>\alpha</math> positive lesions
 
b. FR<math>\beta</math> positive lesions
 
 
 

Exploratory	

 
1. To assess the feasibility of using genomic markers to predict utility of CYTALUX with NIR imaging
 
2. To assess the feasibility of CYTALUX to identify sentinel lymph nodes
 
	
 
1. Genomic evaluation of tumor inclusive of, but not limited to: 
 
a. Estrogen receptor/progesterone receptor (ER/PR) status
 
b. HER2 status
 
c. Mismatch repair (MMR) status
 
d. POLE status
 
e. p53 status
 
f. CARIS whole genome sequencing
 
 
 
2. The exploratory endpoint is the detection rate of CYTALUX with NIR imaging for identification of sentinel lymph nodes (SLNs). The detection rate is the proportion of the patients with SLNs detected by CYTALUX and NIR imaging in all enrolled patients.
 

03 Sep 2025

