#### **8.3.5      *Adverse Event Reporting***

Disease related events expected in this population may be reported by the investigator if they differ in nature or frequency from what is expected and appear to have a causal relationship to the test article. Adverse events must be reported in the subject's source documents. It is the Investigator's responsibility to forward to the site's IRB all SAE/SUSAR/unanticipated ADE reports.

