### **9.2.3 Safety Analyses**

Safety will be described via subject incidence of treatment emergent adverse events (TEAEs) including serious TEAEs as well as adverse device effects (ADEs) considered as causally related.

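### Section 8.3.1 limits documentation to product-related events, but the secondary safety endpoint counts all adverse events

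*Protocol*

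**What the plan says.** The secondary safety endpoint is given in the same terms in the synopsis (Section 1.1), Section 3 and Section 9.1: "Incidence rates of all adverse events (AEs), adverse device effects (ADEs), and SAEs, from the time of CYTALUX administration through Visit 3". It carries no causality restriction.

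Section 8.3.1 begins with a definition that agrees with this. An AE is an untoward occurrence "whether or not considered causally related to that product". The same paragraph then ends with a collection rule that does not agree: "Only AEs and ADEs considered causally related to the investigational product will be documented during the trial period". The section goes on to define an ADE by exposure to a device, here the camera system and its illumination.

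Section 8.3.2 exempts serious events: all SAEs are documented. Section 9.2.3 says safety will be described by the subject incidence of "treatment emergent adverse events (TEAEs) including serious TEAEs as well as adverse device effects (ADEs) considered as causally related". It is unclear whether the closing phrase applies to the ADEs alone or to the whole list.

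**The concern.** An incidence of all AEs cannot be computed from a record that holds only the related ones. If site staff build the case report form from Section 8.3.1, the only explicit statement of scope, the trial would report related-event incidence plus SAEs under the label of all AEs.

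The excluded class is not a negligible one on the protocol's own account. Section 2.4.1 states: "Adverse events in the prior studies have been attributable to the underlying disease or to surgery". Judging relatedness is also hard in this design. Infusion may finish as little as one hour before imaging, and the known reactions in Section 2.4.1 include nausea (13%), vomiting (5%) and abdominal pain (2%), which could also be put down to surgery. If the causality judgement decides whether an event is documented at all, a misattributed event may leave no study record to re-examine.

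There is a second, less certain gap. The filter refers to the investigational product, while ADEs are tied to the device. If the product means the drug, device-only events fall outside the rule even though ADEs are named in the endpoint. Section 2.4.1 recognises such hazards: "The use of a near-infrared fluorescence camera system during surgery may result in contamination of the sterile field or injury due to disengagement".

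**Working it through.** The protocol gives no expected rate or precision for the safety endpoint, so there is no figure to reproduce. The check compares the text and then works out what follows if Section 8.3.1 is applied.

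**Step 1. Do other sections settle the conflict?**

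Pointing to recording regardless of causality:
- Section 1.3 schedules AE assessments at Visits 1, 2 and 3.
- Sections 8.1.2 to 8.1.4 record or ask about events with no filter; for surgery, "AEs and ADEs will be recorded during and following surgery".
- Section 7.1 treats any new clinically relevant finding as a reportable AE.
- Section 8.3.4.2 has a Not Related grade and requires an alternative cause to be documented for such events. That duty makes no sense if they are not documented.
- Section 8.3.5 requires AEs to appear in source documents.

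Pointing to related events only:
- Section 8.3.1, explicitly.
- Section 8.3.5, first sentence, on anticipated consequences of the disease, which it says "may be reported by the investigator if they differ in nature or frequency from what is expected and appear to have a causal relationship".
- Section 9.2.3, at least for ADEs.

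No section says which prevails for non-serious events.

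**Step 2. What can be known under Section 8.3.1?**

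Inputs: n = 10 (Section 1.1); r = number of patients with a documented event, meaning a related AE or ADE, or any SAE. Any of the other 10 − r patients may have had an unrelated non-serious event that was left out. Therefore

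r/10 ≤ incidence of all AEs ≤ 10/10, with width (10 − r) × 10 percentage points.

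| r (assumed) | Range for incidence of all AEs | Width |
|---|---|---|
| 0 | 0% to 100% | 100 points |
| 1 | 10% to 100% | 90 points |
| 2 | 20% to 100% | 80 points |
| 3 | 30% to 100% | 70 points |

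For r = 2 the exact 95% confidence interval is 2.5% to 55.6%. It describes the related-event rate and carries no information about the events left out.

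**Step 3. Illustration of the gap**

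Take 17% as a stand-in for the related-event rate. Section 2.4.1 gives it for adverse reactions during administration in prior studies, so it is only an approximation. Let u be the probability that a patient has an unrelated non-serious AE; the protocol gives no value, so u is assumed over a range. Assume independence and ignore SAEs. Then

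all-AE incidence = 1 − (1 − 0.17)(1 − u).

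| u (assumed) | Incidence of all AEs | Shown under Section 8.3.1 |
|---|---|---|
| 10% | 1 − 0.83 × 0.90 = 25.3% | 17% |
| 30% | 1 − 0.83 × 0.70 = 41.9% | 17% |
| 50% | 1 − 0.83 × 0.50 = 58.5% | 17% |
| 80% | 1 − 0.83 × 0.20 = 83.4% | 17% |

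The documented figure stays at 17% whatever u is, so the collected data cannot tell these situations apart.

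**The case against.** The strongest reply is that most of the operative text already implies unfiltered recording, so the sentence in Section 8.3.1 is a stray one and the events would survive in source documents and medical records. This has force. It means the loss depends on Section 8.3.1 being followed, and that some events might be recovered from charts. It does not remove the defect: the stray sentence is the only explicit rule on scope, and chart retrieval would be of uncertain completeness.

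On devices, it can be said that the sentence names ADEs and that Section 8.3.1 also asks the investigator to consider events in relation to trial procedures, so a drug-only reading is strained. That is fair. The device gap is an ambiguity to close and not an established loss.

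Section 2.4.1 gives no rate for disease- or surgery-related events and does not say they were non-serious. It also reports drug reactions that Section 8.3.1 would capture. The size of the excluded class is therefore unknown. The range from r/10 to 1 would hold for any unrecorded class of event, and Section 9.2.3 promises no confidence interval for safety, so the interval in the working is illustration only.

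Finally, this is a 10-patient, uncontrolled pilot of an approved agent, with descriptive safety as a secondary aim. That limits the consequence but does not make the endpoint computable under the stated rule.

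**Conclusion.** The concern holds. The protocol contradicts itself on which adverse events are collected, within Section 8.3.1 and between that section and the secondary endpoint. Applied as written, the rule leaves the incidence of all AEs identified only from below, and each patient with solely unrelated non-serious events costs 10 percentage points. The actual loss cannot be estimated. It depends on the site following Section 8.3.1 and on how many such events occur.

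The effect is limited to non-serious events judged unrelated and, if the product is read as the drug alone, to device-only ADEs. It should be fixed before enrolment, though it does not threaten the trial's main result. A statistical analysis plan could not repair it, because the rule governs what is collected.

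**What to change.** **Preferred.** Replace the restricting sentence in Section 8.3.1 with a rule that every AE and ADE from the start of infusion through Visit 3 is documented regardless of causality, with relationship to drug, device and surgery recorded for each. Bring the first sentence of Section 8.3.5 into line, and state in Section 9.2.3 that all-cause and related incidence are both reported. The cost is protocol wording and a few extra form entries for 10 patients, at visits that already assess AEs.

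**Minimum, if related-only collection is intended.** Restate the endpoint in Sections 1.1, 3 and 9.1 as related AEs and ADEs plus all SAEs. Say whether related means to the drug, the device or either, and align Sections 8.1.2 to 8.1.4 and 9.2.3. This costs wording only, but the trial would then give no all-cause incidence of non-serious events.

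While these sections are open, also reconcile the two-grade causality scale in Section 8.3.4.2 with the three degrees of relatedness used in Section 8.3.6. This is a minor, separate point.
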